### 5.5.2 RT Delays

RT-related toxicities should be managed as per local practice. RT dose modifications are not allowed per se, but information on managing delays is given in the radiotherapy section (see section 5.7.8). In case of any AEs leading to RT interruption or delays not considered related to either TMZ or MRZ, both drugs should continue as scheduled if medical condition allows it.

### 5.5.3 TMZ

During concomitant treatment part of the study, TMZ-related toxicities should be managed as per local practice. During adjuvant treatment, if the start of treatment cycle needs to be delayed due to TMZ toxicity (not related to MRZ), the planned cycle (TMZ + MRZ) may be delayed for a maximum of up to 14 days. If toxicity persists beyond 14 days, the TMZ treatment will be skipped during this cycle (The start of the cycle begins with the first dose of MRZ treatment and will be administered as scheduled) and TMZ treatment will be resumed with the following cycle.

Dose modifications for TMZ are allowed and should follow the standard of care at the institution. In case of any AEs leading to TMZ interruption (need to skip a treatment dose) and not considered related to MRZ, MRZ should continue as scheduled if medical condition allows it.

The combined TMZ + RT treatment increases incidence of phototoxicity. Patients should be advised to minimize UV light exposure for the duration of the combined treatment and for 1 month after the last RT treatment.

Prior to start of TMZ treatment, patients should be advised on the risk of potential irreversible infertility and/or testicular damage from TMZ and the possibility of sperm conservation.

## 5.6 Concomitant treatments

### 5.6.1 General

Concomitant medications to treat comorbid conditions and AEs are permitted. Enzyme-inducing anti-epileptic drugs (EIAEDs) are allowed. Steroids are allowed and dosing is at the discretion of the Investigator, with their use recorded in the case report form (CRF).

MRZ appears to have a very low potential for drug-drug interactions as it is neither an inhibitor nor an inducer of hepatic cytochrome P450s (CYPs) from different species, it is not influenced by multiple drug resistant/adenosine triphosphate (ATP)-binding cassette transporters and is inactive in a broad array of enzyme, ion channel, second messenger, and receptor assays.

Hydrolysis in the systemic circulation and tissues or gastrointestinal (GI) tract appears to be the major metabolic route for MRZ and the known metabolites are inactive both as proteasome inhibitors and cytotoxic agents.

The use of TMZ can reactivate opportunistic infections including CMV, HSV, HZV and PJP. However, PJP prophylaxis is not recommended as a standard treatment according to current guidelines (Ref. 52). Therefore, treatment will be prescribed as per local standards. If part of local standard of care, prophylaxis against *Pneumocystis jirovecii* can be initiated for patients receiving combined TMZ and RT for the 42-day (maximum 49 days) regimen regardless of lymphocyte count. If lymphopenia occurs, they are to continue the prophylaxis until recovery of lymphopenia to grade  $\leq 1$ .

### 5.6.2 Supportive care in case of toxicity

In Phase 1 studies to date, MRZ has caused clinically significant nausea and vomiting requiring the use of anti-emetics as therapy and also as prophylaxis. In addition, nausea and vomiting are also very commonly associated with TMZ. Therefore, both the therapeutic and prophylactic use of anti-emetics is allowed in this study at the discretion of the Investigator as necessary (may not be needed at the first dose).

To date, MRZ has also caused some hallucinations, therefore both the therapeutic and prophylactic use of anti-psychotics is allowed in this study at the discretion of the Investigator as necessary.

### 5.6.3 Prohibited therapies

The following treatments are NOT permitted during the study treatment:

- Treatment with other systemic anti-cancer agents before disease progression (chemotherapy, immunotherapy, anti-tumor vaccines, targeted agents, or other treatments not part of protocol-specified anti-cancer therapy)
- Concurrent investigational agents of any type before disease progression
- Craniotomy, intra-tumoral interstitial therapy, any surgical procedures under investigation or any form of radiosurgery

Any of the above will lead to patient's discontinuation from study treatment.

Additional treatment with tumor treating fields in the adjuvant setting is discouraged but will not constitute a protocol violation.

Alternative therapies are discouraged and must be discussed with the local investigator.

### 5.6.4 ECG with use of Marizomib

To date, there has been no signal of a safety issue with ECG abnormalities including prolonged QTc with marizomib. There has been no signal of ECG abnormalities in patient treated with marizomib. However, a thorough

analysis of the QT/QTc data has not yet been submitted to the US FDA. Thus additional ECGs will be collected in the marizomib arm of the study.

12-lead ECGs will be collected for all subjects on marizomib at specified timepoints: baseline, Day 1 of concomitant treatment, Cycle 2 Day 1 of adjuvant treatment, and as clinically indicated and will be assessed locally.

ECGs on Day 1 of concomitant treatment and Cycle 2 Day 1 of adjuvant treatment will be collected within 15 minutes after end of MRZ infusion. The standard 12-lead ECGs (including heart rate, PR-interval, QRS, QT interval, and QTc interval) will be performed and recorded.

For subjects enrolled into the marizomib arm prior to the implementation of protocol version 5, 12-lead ECG on Day 1 of the subsequent two cycles of adjuvant treatment within 15 minutes after end of MRZ infusion.

## 5.6.5 Covid-19 vaccines

As per the European Medicines Agency (EMA):

If physicians decide to administer SARS-CoV-2 vaccines in patients enrolled in the study, decisions should be individualized based on the risk of SARS-CoV-2 complications and potential benefit from the vaccine, general condition of the patient and the severity of COVID-19 outbreak in a given area or region and in accordance with the vaccine label. Furthermore, the national guidelines and/or institutional guidelines must be followed.

The available SARS-CoV-2 vaccines, that are not live attenuated vaccines, are not contra-indicated in patients on anticancer treatment.

Treatment schedule should not be altered because of the COVID-19 vaccination.

The administration of a SARS-CoV-2 vaccine (including brand name) shall be added in the concomitant medication form in the eCRF and noted in the patient's medical file. Any possible vaccine related AE should be captured in the AE forms in the eCRFs, specifying the potential relationship to the vaccine.

## 5.7 Radiotherapy

RT will consist of a conventionally fractionated regimen delivering a total dose of 60 Gy in 30 fractions in 6 weeks, a fraction of 2 Gy once daily, 5 days per week. Participating investigators will find the provisions on this chapter summarized in the RTQA Guidelines.

### 5.7.1 Facility and Equipment

Institutions must comply with the Quality Assurance of Radiotherapy requirements and procedures described in detail in the Quality Assurance in Radiotherapy section 17.4.1.

Patients will be treated on megavoltage equipment, i.e. linear accelerator beams with a minimum nominal energy of 6 MV. SAD should be at least 100 cm. Electrons, particles and implants are not permitted. The use of Cobalt units is not allowed in this trial.

The volume should be treated by a multiple field technique, with all fields treated at each fraction

Treatment with a single beam and parallel pair alone are not acceptable.

Treatment with intensity modulated radiotherapy (IMRT) is recommended. It can be used provided it is i) *without simultaneous integrated boost*, ii) conventional fractionation, and iii) the dose prescription and homogeneity criteria are in accordance with ICRU 83 (2010).

3D treatment planning computers and BEV planning should be used. The use of DVH for planning is mandatory. Images, as digital reconstructed radiograph (DRR), should be available for assessment of setup accuracy.

## 5.7.2 Patient position and data acquisition

Patients can be planned and treated supine in a custom made immobilization shell (any fixation system with relocation accuracy  $\leq 3$  mm).

A single phase treatment volume will be used throughout treatment. A cone-down volume or boost volume is not allowed. All margins should be added using a 3D growth algorithm where possible.

The images of the pre-RT MRI, performed with the subject placed in the treatment position (supine), should be used to aid definition of the gross tumor volume (GTV) and the clinical target volume (CTV) on the planning CT without contrast ( $\leq 3$  mm slice thickness). Wherever possible, an image co-registration should be done. Preferably the pre RT MRI should be within 2 weeks of the planning CT otherwise the planning CT should be done with contrast.

## 5.7.3 Volume definition

The definition of volumes will be in accordance with ICRU Reports #50, #62 and #83 [ICRU 1993; ICRU 1999; ICRU 2010].

### 5.7.3.1 Gross Target Volume (GTV)

For subjects whose tumor has been biopsied (open biopsy only; stereotactic biopsy not allowed): the region of enhancement (without edema) on planning CT plus pre-RT MRI.

For subjects whose tumor has been resected: The GTV is the surgical tumor bed plus any residual enhancing tumor as seen on the planning scan. Co-registration of planning CT and pre RT MRI should be performed.

### 5.7.3.2 Clinical Target Volume (CTV)

The GTV plus a margin to account for microscopic spread. This margin will usually be 1.5-2 cm maximum, but can be reduced in anatomical regions where spread is unlikely (e.g. bony structures). The exact GTV-CTV margin is left to the best estimate of each individual investigator; it may depend on various factors such as the tumor location, the previous use of steroids, etc.

In case of complete or subtotal removal, the position of the tumor bed may have shifted, and the CTV should take into account the new position of the abnormality on the planning CT scan and any post-operative imaging.

### 5.7.3.3 Planning Target Volume (PTV)

The PTV (PTV6000) will take into account uncertainties of planning and setup. The margin between CTV and PTV should be based on known departmental values, but will usually be 0.5-0.7 cm.

### 5.7.3.4 Organs at Risk

The following Organs at risk (OARs) will be delineated (Ref. 38). Naming of the structures will follow Santanam *et al.* (Ref. 37):

| OAR                       | Description  |
|---------------------------|--|
| Eye balls                 | The whole of the outside of the globe should be contoured to include sclera and cornea. The macula lies opposite the lens.   |
| Lenses                    | Seen at the anterior part of the globe.  |
| Optic Nerves (if visible) | From the back of the globe to the optic chiasm passing through the optic canal to enter the skull anterior and inferior to the anterior clinoid. Should be delineated in continuity with the optic chiasm. |

| OAR                                    | Description  |
|--|--|
| Optic Chiasm                           | Sits above and behind the anterior clinoids and runs backwards above the sella turcica. The anterior and posterior 'limbs' should extend 5 mm to include the start of the optic nerves anteriorly and optic tracts posteriorly. The chiasm can sometimes only be seen on a single slice as it is about 3 mm thick in craniocaudal direction. |
| Lacrimal Glands                        | Situated in the upper lateral region, above the lateral rectus muscle, partly on top of the eyeball.   |
| Internal ear                           | Sit just anterior to the lateral aspect of the internal auditory canal.  |
| Brain Stem                             | The foramen magnum to the point where the optic tract passes lateral to the midbrain   |
| Brain**                                | Whole brain parenchyma includes all intracranial contents, inclusive of target volumes.  |
| Whole Brain minus PTV                  | For ease of DVH calculation.   |
| Contralateral normal brain             | To be delineated for tumors not crossing the midline.  |
| Optic Nerve Planning Risk Volume (PRV) | Optic Nerves expanded by volumetric 3 mm   |
| Optic Chiasm PRV                       | Optic Chiasm expanded by volumetric 3 mm   |

\*\* Please do not include the brainstem in the contour of the contralateral brain, brain and brain –PTV contours

### 5.7.4 Dose

Dose prescription and recording should be according to ICRU 83 criteria. This also applies if the treatment is delivered by 3D-CRT.

The PTV should be encompassed by the 95% isodose. However, if the PTV is in close proximity to an OAR the 90% isodose is acceptable provided 98% of the PTV receives at least 90% of the prescribed dose.

The regimen consists of a total dose of 60 Gy in 30 daily fractions, for a total overall time of 6 weeks. The time interval between fractions should be at a minimum of 18 hours, with an acceptable variation of  $\pm 2$  hours on weekdays, and a maximum interruption of 72 hours ( $\pm 2$  hours) for weekends or public holidays. The time of day of the RT should, if possible, be kept the same each day. This will also facilitate the delivery of TMZ and MRZ.

### 5.7.5 Treatment planning

The following are mandatory:

- Planning CT scan and pre-RT MRI is required for simulation and planning.
- Three-dimensional treatment planning computers and BEV planning.
- A dose calculation grid of 3 mm or less should be used.
- The use of DVH for planning.

#### 5.7.5.1 Dose Limitations to Critical Structures

Whenever possible, attempts should be made to limit the maximum dose for the OARs as follows:

- Optic Chiasm:  $\leq 55$  Gy. to 0.03cc

- Optic Chiasm PRV  $\leq 55$ Gy to 0.03cc
- Brainstem:  $\leq 56$  Gy. to 0.03cc
- Optic Nerves  $\leq 56$  Gy to 0.03cc
- Optic Nerves PRV:  $\leq 56$  Gy. to 0.03cc
- Eye balls, retina:  $\leq 40$  G to Dmax
- Lens: 10 Gy to 0.03cc
- Lacrimal glands:  $< 40$  Gy to 0.03cc
- Cochlea:  $\leq 45$  Gy if both sides are involved; otherwise  $\leq 60$  Gy. (Low priority OaR) to 0.03cc
- The dose to the normal brain minus the PTV should be kept as low as possible. The Dmean is to be  $\leq 30$  Gy

Dose to the contra-lateral normal brain should be Dmean  $\leq 30$ Gy, except where the tumor or the PTV margin cross midline. If required, supplementary shielding of OAR is allowed, even if it lowers the dose to a part of the PTV.

### 5.7.6 Treatment verification and accuracy

Treatment verification shall be performed at least weekly, preferably using an electronic portal imaging device (EPID), according to the standard correction protocol of the participating institute.

Copies of portal imaging used for verification should be available upon request.

### 5.7.7 Complications

Expected acute toxicity of conventional RT include headache, fatigue, hair loss, skin reaction, occasionally nausea, mucositis (if nasopharynx included), temporary reduced hearing (if ear canal included), and temporary loss of taste (if nasopharynx included).

Depending on the tumor location and the region to be irradiated, several tissues or organs are potentially at risk for late damage, such as cortical brain, brain stem, chiasm, ear (mid or internal), lachrymal gland and pituitary gland. All efforts should be made during planning to minimize the dose to critical structures.

Late complications will be recorded according to CTC version 5.0.

### 5.7.8 Treatment interruptions/modifications

No RT dose adjustments are recommended for treatment interruptions. Maximum overall treatment time should be  $\leq 49$  days. If radiotherapy is delayed, MRZ and/or TMZ should be held until radiotherapy treatment resumes. Should radiotherapy be held for longer and if it is believed to be of clinical benefit for the patient to restart RT + TMZ  $\pm$  MRZ, sites should contact the medical monitor.

Reasons for treatment interruption include major worsening of neurological or mental status or any other medical condition that would preclude the continuation of RT. The decision for interruption and resumption of RT after interruption will be taken on an individual basis by the local investigator.

**Dose adjustments or transient discontinuations of RT should be avoided** as much as possible. In individual cases the treating radiation oncologist will discuss with the study coordinator whether lowering of the total tumor dose is necessary.

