## 5.1.2 Temozolomide

Temozolomide (TMZ) is an approved drug for the treatment of patients with newly diagnosed glioblastoma. TMZ is available commercially and will therefore be taken off the shelf.

During radiotherapy, TMZ is administered at a dose of 75 mg/m^2 daily, starting at the first day of radiotherapy, typically for 42 days and for a maximum of 49 days. Four weeks after the last day of radiotherapy, treatment with TMZ is resumed at a dose of 150 mg/m^2 (cycle 1) and 200 mg/m^2 (subsequent cycles) daily for 5 days every 28 days (corresponding to a cycle) for up to 6 cycles. TMZ will be administered and prescribed according to the official label and the standard of care which has been defined in a previous EORTC/NCIC trial (Ref. 42).

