## 8.2 Statistical analysis plan

### 8.2.1 Analysis populations

- Intention-to-treat population (ITT): All randomized patients will be analyzed in the arm they were allocated by randomization.
- Per protocol population (PP): All randomized patients who are eligible and have started their randomized treatment arm. Patients with major protocol deviations as defined in the medical review plan are also excluded from the PP population.
- Safety population (SP): All randomized patients who have started any treatment arm i.e. if a patient received treatment arm other than the patient's randomized treatment arm, then the patient will be assigned to the treatment arm that the patient actually received during the study in the analysis.
- Patients who did not start any treatment arm are excluded from PP and SP.
- Patients excluded from PP or SP will be reported in separate tables with the reason(s) of exclusion.
- Subgroups: The following subgroups will be defined: MGMT methylation status (uMGMT, mMGMT, unknown/missing), age ( $\leq 55$ ,  $> 55$  years), gender (male, female), Karnofsky performance status (70/80, 90/100), baseline steroid use (yes, no), extent of surgery (partial/biopsy, gross total).

A patient will be considered to be eligible if he/she did not have any deviation from the patient entry criteria listed in chapter 3 of the protocol. Potential eligibility problems will be assessed by the Clinical Research Physician at time of medical review.

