10.4. Relative Dose Intensity

Relative dose intensity is the dose intensity divided by the planned dose intensity.

The planned dose intensity is

$$\begin{aligned} & \text{Planned dose intensity}_{\text{Conc TMZ or MRZ}} \\ &= \frac{42 * 75 \frac{\text{mg}}{\text{m}^2} \text{ of TMZ or } 5 * 0.8 \frac{\text{mg}}{\text{m}^2} \text{ of MRZ}}{\text{Theoretical duration of one cycle (weeks)} = 6 \text{ weeks}} \end{aligned}$$

$$\begin{aligned} & \text{Planned dose intensity}_{\text{Main TMZ}} \\ &= \frac{(150 \frac{\text{mg}}{\text{m}^2} \text{ at cycle 1} + \sum_1^N (n - 1) * 200 \frac{\text{mg}}{\text{m}^2}) / N \text{ of TMZ}}{\text{Theoretical duration of one cycle (weeks)} = 4 \text{ weeks}} \end{aligned}$$

$$\begin{aligned} & \text{Planned dose intensity}_{\text{Main MRZ}} \\ &= \frac{3 * 0.8 \frac{\text{mg}}{\text{m}^2} \text{ of MRZ}}{\text{Theoretical duration of one cycle (weeks)} = 4 \text{ weeks}} \end{aligned}$$

Relative dose intensities will be categorized into < 60%, 60% to <80%, 80% to <90%, 90% to <110%, and \geq 110%, and frequency counts will be provided by treatment arm.

For RT, the (relative) dose intensity is not meaningful. The number of subjects with cumulative dose >90%, \leq 90% of the planned total dose (60 Gy) will be summarized by treatment arm.

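### For radiotherapy interruptions caused by an adverse event unrelated to either drug, Protocol 5.5.2 says to continue both drugs, 5.7.8 says to hold, and neither takes precedence

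*Protocol*

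**What the plan says.** Protocol 5.5.2 (RT Delays) gives a conditional rule: "In case of any AEs leading to RT interruption or delays not considered related to either TMZ or MRZ, both drugs should continue as scheduled", provided the patient's medical condition allows it. The same paragraph tells the reader that "information on managing delays is given in the radiotherapy section (see section 5.7.8").

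Protocol 5.7.8 (Treatment interruptions/modifications) gives a general rule: "If radiotherapy is delayed, MRZ and/or TMZ should be held until radiotherapy treatment resumes". On what can stop RT it says: "Reasons for treatment interruption include major worsening of neurological or mental status or any other medical condition that would preclude the continuation of RT". It does not refer back to 5.5.2.

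On analysis, Protocol 8.2.1 says: "Patients with major protocol deviations as defined in the medical review plan are also excluded from the PP population". SAP section 8 plans a summary of violations by arm and a listing. SAP 10.3 to 10.5 plan dose intensity, relative dose intensity, and by-arm tables of RT and drug interruptions with their reasons.

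**The concern.** A site that consults the dose-modification section would keep giving drug. A site that consults the radiotherapy section, or follows the cross-reference to it, would stop. Both would be acting on the protocol's text, for the same event in the same kind of patient.

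Three things are at stake. Patients with the same event may have been managed differently, for a reason that has nothing to do with their condition. A reviewer of violations has no text from which to decide whether holding or continuing was the departure. And a reader of the exposure tables cannot tell drug held on the protocol's instruction from non-adherence. The trial is open-label, and MRZ is given in one arm only, so it should not be assumed that case-by-case judgements would fall evenly across the arms.

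**Working it through.** The point rests on text, so the first step is to set the two sections side by side.

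| | Protocol 5.5.2 | Protocol 5.7.8 |
|---|---|---|
| Trigger | RT interrupted or delayed by an AE not considered related to TMZ or MRZ | RT delayed, any cause |
| Instruction | Continue as scheduled | Hold until RT resumes |
| Condition | Patient's medical condition allows | None |
| Drugs | Both | MRZ and/or TMZ |
| Link to the other section | Refers to 5.7.8 | None |
| Precedence | Not stated | Not stated |

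The second step is to find where the two rules meet.

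1. RT delayed for a reason other than an AE: 5.5.2 gives no instruction to continue. Only 5.7.8 applies, so there is no conflict.
2. RT interrupted by an AE related to TMZ or MRZ: this is outside 5.5.2's rule, so there is no conflict.
3. RT interrupted by an unrelated AE, patient not fit for drug: 5.5.2's proviso fails, so there is no conflict.
4. RT interrupted by an unrelated AE, patient fit for drug: 5.5.2 says continue and 5.7.8 says hold. This is the conflict.

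Case 4 is not ruled out by the kinds of event that 5.7.8 has in mind, because its list of reasons extends to any medical condition that precludes RT. The wording of 5.7.8 also leaves open whether one or both drugs are held. It may say and/or only because control patients receive no MRZ. On either reading at least one drug stops that 5.5.2 would keep going.

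Appendix L (section 2.2) does not settle the matter. It sends skipped or interrupted treatment back to chapter 5, which contains both rules.

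The third step is an illustration of what the choice does to reported exposure. There is no document figure for this to reproduce beyond the planned intensity. Assumption: a 7-day RT interruption that takes RT from 42 to 49 days. Protocol 5.1.2 gives concomitant TMZ "typically for 42 days and for a maximum of 49 days", at 75 mg/m² daily. SAP 10.1 defines duration as last minus first dose date plus one day, in weeks.

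- Planned intensity (SAP 10.4): 42 × 75 / 6 = 525 mg/m² per week.
- TMZ held for 7 days, then resumed to the end of RT: 42 × 75 / 7 = 450. Relative intensity is 450 / 525 = 85.7%.
- TMZ continued to day 49: 49 × 75 / 7 = 525, or 100%. If it stopped at day 42 as scheduled: 42 × 75 / 6 = 525, also 100%.

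SAP 10.4 states: "Relative dose intensities will be categorized into < 60%, 60% to <80%, 80% to <90%, 90% to <110"%, with a top class above that. The patient falls in the 80% to <90% class if TMZ was held and in the 90% to <110% class if it was continued. Each figure is well defined. What the table does not show is whether the difference came from following one section or the other.

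**The case against.** The strongest reply is that 5.5.2 is a narrow exception to the general rule in 5.7.8, and that a specific rule ordinarily prevails. That is a possible reading, but neither section says so, and 5.5.2 points to 5.7.8 for managing delays without claiming to override it. The reply also notes that many reasons for stopping RT, such as major neurological worsening, would leave the patient unfit for drug. That stands, and it narrows the subset.

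Several stronger readings are tempting, and the documents do not support them.

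- A reader might infer that every RT interruption is affected. Cases 1 to 3 above show otherwise.
- A reader might infer that the same conduct is both compliant and a deviation, with loss from the per-protocol (PP) population to follow. No section classifies either conduct. Major deviations are defined in the medical review plan, which is not among the documents.
- A reader might infer that dose intensity becomes undefined. SAP 10.3 and 10.4 compute it from dose given and time elapsed. Deviation status does not enter.
- A reader might take 49 minus 42 days, and one MRZ dose, as an upper limit on the drug in question. Section 5.7.8 itself provides for RT being held for longer. In the other direction, MRZ is scheduled on days 1, 8, 15, 29 and 36, so a one-week interruption within days 16 to 28 meets no MRZ dose.

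It is also fair to say that SAP 10.5 already tabulates RT and drug interruptions with reasons by arm, so inconsistent handling would be partly visible. And with all 749 patients randomized and recruitment closed (Protocol 8.4), treatment due to start within a week of randomization and RT meant to finish within 49 days, a clarification now will change the concomitant treatment of few patients, if any.

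**Conclusion.** The conflict is real and confined to one subset: RT interrupted or delayed by an AE not considered related to TMZ or MRZ, in a patient whose condition allows drug. In that subset the two rules cannot both be followed. Its size cannot be given, because the documents report no count of RT interruptions by cause.

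The primary analysis of overall survival is by intention to treat and does not change. The remaining effect is on the violation summary and listing, on how exposure is interpreted, and possibly on PP membership. The PP repeat of the efficacy analyses is run only if exclusions exceed 10% in at least one arm (Protocol 8.2.4, SAP 11.4). The PP repeat of the quality-of-life analysis (Protocol 10.5.2, SAP 13.6.2) states no such threshold. Whether either depends on this point turns on the medical review plan.

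**What to change.** The sponsor's clinical team should reconcile Protocol 5.5.2 and 5.7.8 into a single instruction. That instruction should say which causes of RT delay it covers and whether it applies to one drug or both. Which instruction is right is a clinical decision, and none is proposed here.

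Because recruitment is closed, the statistical part matters more. Before the PP population and the violation listing are finalised, the sponsor should state that patients in this subset managed under either wording are classified in the same way in both arms. It should also flag these interruptions in the exposure summaries, so that a lower relative dose intensity from drug held under 5.7.8 can be recognised.

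The cost is a short protocol clarification, one statement in the medical review plan or a SAP note, and a flag built from the RT-interruption and drug-interruption reasons that SAP 10.5 already plans to summarise.
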